5.1 Serious Adverse Events

A Serious Adverse Event (SAE) is defined as any unfavourable medical event which, at any dose, results in one of the following:

- Leads to patient's death;
- May lead to a fatal outcome in the short term;
- Leads to subject's hospitalisation or prolonged hospitalisation;
- Causes significant or persistent disability/incapacity;
- Another significant medical event.

Significant medical events that do not lead to the patient's death, or are not life-threatening, or do not require hospitalisation, may nevertheless be considered serious adverse events when, based on appropriate medical judgement, they may pose a risk to the subject's health or may require medical or surgical intervention to prevent one of the *outcomes* described above.

Hospitalisation is defined as the subject's stay (usually for at least one night) in a hospital or Accident and Emergency Room for observation and/or treatment. When it is uncertain whether hospitalisation occurred or was necessary, the adverse event must be considered serious.

Hospitalisation for elective surgery or for *routine* clinical procedures that are not the consequence of an adverse event should not be considered an adverse event. If an unfavourable event is reported during the procedure, it must be reported as an adverse event; whether this is "serious" or "non-serious" will be decided based on the usual criteria.

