5.2 Reporting of Adverse Events and Serious Adverse Events

All adverse events reported by the subject or observed by the investigator or by a member of his/her *team* will be reported in the Serious Adverse Event Form. The following information must be collected for each adverse event:

- onset and resolution date and time (duration);
- seriousness (defined subsequently in the text);
- any required treatments or interventions adopted;
- *outcomes*;
- relationship to the product used in the trial (defined subsequently in the text);
- if the adverse event has caused the subject to withdraw from the Study.

All adverse events must be recorded using the accepted diagnoses, where possible. Any abnormal laboratory results, vital signs or abnormalities detected at the physical examination must not be recorded as adverse events if it is known that they are a symptom or sign of a syndrome or a diagnosis already reported as such. For example, ST-segment elevation detected by ECG and increased serum creatine phosphokinase are both known signs of myocardial infarction; therefore, they need not be reported if myocardial infarction was already reported as an adverse event. However, if both occur separately and no myocardial infarction was diagnosed, then this event must be reported as an adverse event.

Seriousness categories and the causal relationship of adverse events must be defined using the parameters listed below:

Seriousness:

| | |
|----------|---|
| mild | easily tolerated, does not hinder normal activities of daily living |
| moderate | partially hinders activities of daily living |
| serious | fully hinders all activities of daily living |

Relationship with the Study procedures:

Not related: the temporal relationship between the adverse event and the use of the Study product is such that a reasonable relationship between the two is very unlikely.

Possibly related: the adverse event occurs in a time sequence consistent with the start of use of the Study product, but it may also be attributed to the subject's clinical status or to the Study procedures/requirements.

Definitely related: the adverse event occurs in a time sequence consistent with the start of use of the Study product, disappears after its discontinuation and appears again when it is resumed.

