In addition to being recorded in the Case Report Form (*CRF*), serious adverse events (SAEs), which include suspected unexpected serious adverse reactions (SUSARs), must be reported by the investigator on the "Serious Adverse Event Report Form". This form must be completed and sent to the Study Coordinator immediately, i.e. within 24 hours from the detection of the SAE by the research staff. The original must be sent and a copy stored at the trial site.

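### Section 5.2 grades seriousness by interference with daily living, which conflicts with the outcome-based definition in 5.1 and can misclassify serious events in the safety endpoint

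*Combined protocol and SAP*

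**What the plan says.** Section 5.1 sets an outcome test: "A Serious Adverse Event (SAE) is defined as any unfavourable medical event which, at any dose, results in one of the following". The list that follows covers death, a possible fatal outcome in the short term, hospital admission or prolongation of a stay, disability, and other medically important events. Admission is sufficient by itself ("Leads to subject's hospitalisation or prolonged hospitalisation"), a stay for observation counts, and doubt is resolved towards seriousness: "When it is uncertain whether hospitalisation occurred or was necessary, the adverse event must be considered serious".

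Section 5.2 lists six items to collect for each adverse event. One is seriousness, which it says is defined later in the text. The definition it then gives is not the one in 5.1: "Seriousness categories and the causal relationship of adverse events must be defined using the parameters listed below". The table below that sentence has three grades, mild, moderate and serious, separated only by how far the event interferes with daily living. The serious grade is an event that "fully hinders all activities of daily living".

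Two further statements depend on these definitions. At its end, 5.2 requires SAEs to be sent to the Study Coordinator "within 24 hours from the detection of the SAE by the research staff". Section 6, under the analysis of secondary endpoints, has adverse events handled and analysed by the 5.2 criteria and does not cite 5.1.

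On forms, 5.2 first says that all adverse events "will be reported in the Serious Adverse Event Form". It later says that SAEs go on a Serious Adverse Event Report Form. It does not say whether these are the same form.

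**The concern.** Severity (how intense an event is) and seriousness (whether it had or threatened a defined outcome) are separate attributes. Section 5.2 puts a severity scale under the name of seriousness, lists no separate severity item, does not refer back to 5.1, and does not say which rule prevails. One word therefore carries two definitions in adjacent sections.

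What is at stake is the safety endpoint. Treatment safety is the first secondary endpoint (4.3 and 6), the device has no CE marking (1.1 and 2), and the study is multicentre (4.1). A count of serious events is a natural summary of such data, and as written it could be built from either definition.

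**Working it through.** No arithmetic applies. The claim concerns two definitions and depends on no rate, effect size or sample size. The check is to set the definitions side by side and see where they part.

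**Step 1. Compare the criteria.** The 5.1 test asks what the event led to or threatened. The 5.2 test asks how much of daily living it prevented. Neither implies the other.

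| Event | 5.1 | 5.2 grade | Agree? |
|---|---|---|---|
| One night in hospital for observation, daily activities partly limited | SAE (admission) | moderate | No |
| Short event that stops all daily activity, with no admission, lasting disability or significant medical risk | need not be an SAE | serious | No |
| Admission, with all daily activity stopped | SAE | serious | Yes |
| Daily activities partly limited, no 5.1 outcome | not an SAE | moderate | Yes |

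The first two rows follow directly from the text. The mismatch runs both ways: the 5.2 grade understates the first event and overstates the second.

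**Step 2. Ask which definition the data would carry.** Of the six items that 5.2 requires per event, only one is about seriousness, and it is tied to the daily-living table. None asks directly whether a 5.1 criterion was met. The items on interventions and outcomes might let someone reconstruct 5.1 status afterwards, but the plan does not say that this will be done.

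**Step 3. Ask which definition the analysis uses.** Section 6 points to 5.2. A programmer following that reference meets the daily-living table as the only stated definition of the seriousness categories. Section 5.2 also contains the SAE reporting rule, so the reference does not exclude 5.1 status altogether, but it does not call for it either.

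**Step 4. Ask what triggers the 24-hour report.** The trigger is the term SAE, which is defined once, in 5.1. The 5.2 table neither uses nor redefines that term. Read in the ordinary way, an admitted patient whose event is graded moderate still has an SAE and is still reportable within 24 hours. The deadline is at risk only if an investigator uses the 5.2 grade in place of the 5.1 definition.

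**Step 5. Ask whether the forms settle it.** If the two form names mean one form, a literal reading sends every adverse event within 24 hours and no SAE is missed. If they are two forms, 5.2 still separately requires the second for SAEs. Neither reading causes delay by itself. Neither reading corrects the seriousness scale.

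**The case against.** The strongest reply is that this is one mislabelled word. The text appears to be translated (the introduction carries English glosses of Italian institution names), and a mild-to-serious scale based on daily living reads naturally as a severity scale. An investigator would use 5.1 to decide what is an SAE and the 5.2 table to grade intensity. Section 5.1 supports this by treating serious versus non-serious as a two-way decision. Safety also has no pre-specified test in section 6, so no inferential result depends on the label.

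Much of this stands. A labelling error is a fair description of the likely cause, although the documents do not establish it. It does not remove the defect: 5.2 makes its table mandatory as the definition of the seriousness categories, section 6 points to 5.2, and no other text corrects it.

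Three stronger readings are tempting and are not supported:

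- A reader might infer that 5.2 keeps true serious events out of 24-hour reporting. The trigger is the 5.1 term, so this needs an investigator to substitute one rule for the other.
- A reader might infer that sites will in fact count serious events differently. The text permits this, but nothing in the documents shows that it would happen.
- A reader might infer that the adverse-event form itself carries the wrong scale. The form is not in the documents. The scale is protocol text, and the form may already have a separate seriousness item.

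**Conclusion.** The conflict is real and stands in the current text. As written, 5.2 grades seriousness on a severity scale, and section 6 carries the 5.2 criteria into the safety analysis, so serious events can be misclassified in both directions. The effect on the 24-hour rule is secondary and depends on an investigator using the 5.2 grade as the trigger.

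The size cannot be stated as a proportion, because the documents give no adverse-event or admission rates. What can be said is which events are affected: those that meet a 5.1 criterion without fully stopping daily activity, and those that fully stop daily activity without meeting one. The primary endpoint, wound-area reduction at week 10, is not affected.

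The conclusion assumes that the documents are read as written and that no form or instruction outside them already separates the two attributes. The point should be corrected, but it does not undermine the design.

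**What to change.** 1. In 5.2, rename the daily-living scale as severity, with grades mild, moderate and severe.
2. Add seriousness as a separate yes/no item for every adverse event, judged only by the protocol's own 5.1 criteria.
3. Make the 24-hour rule in 5.2 and the safety analysis in section 6 refer to that item, so that reported and tabulated serious events are the same set.
4. Reconcile the Serious Adverse Event Form, now used for all adverse events, with the Serious Adverse Event Report Form. State whether they are one form or two, and which events go on each.

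The cost is minor rewording in 5.2 and section 6 and, if the form does not already have it, one extra field. Treatment, visits and sample size do not change, and no new criterion is introduced.

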4.3 Secondary endpoints

The following secondary endpoints were identified for this study:

1. Treatment safety.
2. Outcomes comparison in terms of the percentage reduction of the area of the wound treated with the EmoLED device versus the wound treated with SOC only within the ten-week observational period.
3. Evaluation of difference in healing time between the two areas.
4. Pain reduction (with pre-treatment assessment on a 0-10 VAS)
5. Depending on the patient's willingness to continue to go to the study site, the observation of any unhealed area(s) over the 10-week period can be extended until complete healing or up to 20 weeks.

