5.3 Safety follow-up of subjects who have withdrawn from the Study

Subjects who have withdrawn from the trial after treatment with the Study device for any reason will undergo ongoing monitoring of any existing adverse events until the findings of the tests related to the adverse event and required by SOCs have returned to baseline values, or until the investigator has verified that these events are no longer clinically significant.

Subjects who exhibit adverse events up to thirty days after the last visit or the last *follow-up* (whichever occurs last) will be monitored until the findings of their tests have returned to baseline values, or until the investigator has verified that the results are no longer clinically significant.

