Adverse event reports will be collected, analysed and managed according to the criteria indicated in 5.2. The most appropriate statistical instrument will be chosen for analysis based on the number and type of adverse events reported.

2. Outcomes comparison as percentage reduction of the area of the wound treated with the EmoLED device versus the wound treated with SOC alone during the 10-week observation period.

Both the areas of the wound treated with the EmoLED device and those not treated with the EmoLED device, as measured on the required observation days, will be considered. A statistical analysis of paired data will be

performed using repeated measurements. In particular, both a comparison of the measurements obtained on different days, separately, and an analysis that will take into account the global trend over the observation period, will be performed.

Tests for data paired to pairs of measurements obtained on different observation days will be performed in the first case. These tests will be applied separately to the various days, evaluating any significant differences in both treated and untreated areas. The adopted statistical test will be either a parametric (t-test) or a non-parametric test (Wilcoxon signed-rank test) depending on the observed data distribution. The statistical significance will be corrected for multiple comparisons (e.g., given the possibility of a positive correlation between the identified measurements, Benjamini-Hochberg correction will be considered).

In the second case, the area under the curve (AUC) will be evaluated for each subject and in each area in order to obtain information on possible differences between changes in the treated and untreated areas of the wound. Either parametric or non-parametric paired data tests (depending on parameter distribution) will be performed in order to evaluate any differences in the trends of this parameter summarising the healing dynamics both in the treated and untreated areas.

The mean value observed in the remaining subjects will be used for both approaches if there is any missing data. A sensitivity analysis will be performed using both the best value and the worst value observed in the subjects.

3. Evaluation of the difference in healing time between the two areas.

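### The top causality level requires recurrence on re-exposure, so irreversible, treatment-ending and late device events can be graded no higher than 'possibly related'

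*Combined protocol and SAP*

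**What the plan says.** Section 5.2 makes its scale binding: "the causal relationship of adverse events must be defined using the parameters listed below". It offers three levels and no others.

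- **Not related** rests on timing alone. The timing must be such that "a reasonable relationship between the two is very unlikely".
- **Possibly related** needs timing consistent with use of the product, "but it may also be attributed to the subject's clinical status or to the Study procedures/requirements".
- **Definitely related** needs consistent timing, and the event "disappears after its discontinuation and appears again when it is resumed".

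There is no intermediate level such as 'probably related'. There is no rule for events that cannot resolve or are not followed by further exposure, and the document contains no second causality scale.

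The scale feeds an endpoint. Section 4.3 lists "Treatment safety" as the first secondary endpoint. For that endpoint section 6 states: "Adverse event reports will be collected, analysed and managed according to the criteria indicated in 5.2". The statistical method is left open until the number and type of events are known.

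**The concern.** A causality scale should let an investigator record that the device plainly caused an event. Here the top level can be reached only through a positive dechallenge followed by a positive rechallenge. That excludes events that cannot resolve and events after which exposure does not recur. The serious adverse event definition in section 5.1 includes death and persistent disability, so the scale is least able to grade the gravest harms.

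This matters because safety is the first secondary endpoint, and section 2 links the safety reports to the device's lack of CE marking. A summary by causality level would put an evident device injury in the same row as an event that merely happened at a compatible time. Unless source records are re-adjudicated, that distinction cannot be recovered once the data are in.

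**Working it through.** No figure in the plan is in question and no arithmetic applies. The check reads each definition as a set of conditions and tests types of event against them.

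**Conditions, from section 5.2**

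- Not related: the timing makes a link very unlikely.
- Possibly related: the timing is consistent, and another attribution is open.
- Definitely related: the timing is consistent, and the event resolves on stopping, and it recurs on resuming. All three are required.

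**Cases.** In every row the timing is consistent, so 'not related' fails throughout.

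| Event | Plausible alternative? | Possibly | Definitely |
|---|---|---|---|
| Lasting injury to the irradiated area | No | Fails: no other attribution | Fails: does not resolve |
| Death | No | Fails: no other attribution | Fails: cannot resolve or recur |
| Event that ends treatment | No | Fails: no other attribution | Fails: nothing is resumed |
| Event after the last irradiation | No | Fails: no other attribution | Fails: nothing is resumed |
| Any of the above | Yes | Met | Fails, as above |
| Transient reaction that settles between visits and returns at the next irradiation | No | Fails: no other attribution | Met |
| Coincidental event, clearly due to another cause | Yes | Met | Fails unless it happens to resolve and recur with treatment |

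**Results**

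1. In the first four rows none of the three levels is met on a literal reading. A site obliged to choose would have only 'possibly related' as a workable option.
2. Where a plausible alternative exists, the same types of event are 'possibly related' by definition.
3. The last row lands in 'possibly related' too, because 'not related' depends only on timing. The middle level therefore collects evident device events from above and coincidental events from below.
4. The sixth row shows that the top level is not empty by construction.

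**Are the excluded cases foreseeable?** The plan provides for them. Section 5.2 asks whether an event led to withdrawal, and section 5.3 says: "Subjects who have withdrawn from the trial after treatment with the Study device for any reason will undergo ongoing monitoring". The same section covers events up to thirty days after the last visit or follow-up. Thermal injury is conceivable, since section 1.1 gives 45°C to 50°C on the treated area. It also reports that 40°C was never exceeded in ulcers, but from isolated observations. Section 5 itself does not expect adverse events. The point does not depend on how likely they are, only on how one would be graded.

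**The case against.** The strongest reply is that the scale works in practice and nothing is lost.

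- **'Possibly related' is broad.** It asks only that another attribution be open, not that another cause be shown. Every treated area is a chronic ulcer that is cleaned, debrided where necessary, dressed and compressed, so most local events would qualify. The scale is headed as a relationship with study procedures, and irradiation could itself be counted as one. This stands. A reader might infer that an evident device injury routinely falls outside the scale. That follows only on the literal reading, for an event with no plausible alternative. The broader reading does not cure the defect, because the event still cannot rise above 'possibly related'.
- **Re-exposure is routine.** Section 4.1 has the device used at each visit, and visits run weekly from W0 to W10. A reader might infer that the number of 'definitely related' events will be close to zero whatever the device does. The documents do not support that: a transient reaction that settles and returns at the next visit can qualify without any exceptional re-exposure.
- **Events are captured regardless of cause.** Section 5 defines adverse events without requiring a causal link. Section 5.2 collects dates, outcome, interventions and any withdrawal. Serious events go to the Study Coordinator within 24 hours, with no causality condition. This also stands, and it limits the harm to grading.
- **No inference on the top level is planned.** A reader might compute an upper confidence limit from a zero count of 'definitely related' events and call it uninformative. Section 6 plans no such limit and does not make that count the safety result.

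**Conclusion.** The point holds as a defect of classification. Irreversible or fatal events, events that end treatment, and events after the last irradiation can never be graded above 'possibly related' under section 5.2, and section 6 carries that grading into the safety endpoint. Events are under-graded, not lost.

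The size cannot be expressed as a number, because the documents give no expected rate or type of device-related event. The effect is confined to the causality breakdown; the total count of adverse events is unaffected.

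Two assumptions are involved. First, the levels are applied as written, which section 5.2 requires. Second, the interval between weekly irradiations counts as discontinuation, which the plan does not state. If it does not count, the top level becomes harder to reach and the defect is wider; the conclusion for the excluded event types is the same either way. The change is worth making before data are collected, but it does not threaten the trial's efficacy conclusions.

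**What to change.** Replace the three definitions in section 5.2 with levels that are mutually exclusive and exhaustive and do not require rechallenge, applied in this order:

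1. **Not related:** the time course makes a link with the device very unlikely, or the event is clearly explained by another cause.
2. **Possibly related:** not excluded by level 1, and a credible alternative cause exists.
3. **Related:** not excluded by level 1, and no credible alternative cause exists.

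Applying them in order gives each event exactly one level. The same phrase, a credible alternative cause, must separate levels 2 and 3. If the top level instead asked for no *more plausible* alternative, an event with an equally plausible or weaker alternative would satisfy both.

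Record dechallenge and rechallenge findings, where they happen to occur, as supporting information that does not determine the level. State in section 6 that 'related' and 'possibly related' events will be reported separately and combined.

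The cost is rewording one short block of definitions, one added sentence in section 6, and a matching change to the adverse event form if it lists the levels (the form is not in the documents). The downside is that a few more events will be classed as device-related. The change concerns recording and reporting only and leaves treatment and patient management as they are.
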